### III C. APPROACH

**IIIC.1 Overview:** The conceptual model guiding our study is presented in **Fig 1**. Aim 1 will assess the effects of PAAS on the magnitude of Phase 2 functional connectivity between reward-drive and cognitive-control neural circuitry at rest and during a decision-making task after controlling for pre-intervention (Phase 1) levels. Aim 2 will evaluate if Phase 2 post-treatment neural circuitry changes mediate PAAS' effects on psychological processes (i.e. cognitive and emotional self-regulation) at the 3-month follow-up (Phase 3) after controlling for Phase 1 values. Our overarching hypothesis is that the functional connectivity between reward and cognitive-control networks correlates with self-regulation, and that PAAS increases the magnitude of functional connectivity between these neural networks. In addition to these hypotheses, we will identify characteristics (demographic, neurobiological, psychological, behavioral and social-contextual factors) that moderate PAAS' effects on the relationship between functional brain changes and cognitive-emotional self-regulation in exploratory analyses (IIIC.3b; **Fig 2**).

A total of 128 AA volunteers (ages 11-13 years, 50% male and female) and 128 parents (primary caretakers) will be recruited. Youth and parents will complete assessments on intervention targets (i.e. parenting processes, youth psychological protective factors and cognitions/behaviors associated with HIV and SUD vulnerability). fMRI scans will be acquired in the youth to assess functional connectivity between reward-drive and cognitive-control neural circuitry during rest and while performing a decision-making task involving probabilistic monetary rewards. A second task that assesses general impulsivity/motor response inhibition (in contrast to reward-drive) will be included as a supplementary measure. Following assessments, the families will be randomized to either PAAS or a wait-list control condition for 6 weeks. fMRI scans will be repeated after 6 weeks to measure functional brain changes from pre-to-post intervention. They will repeat the intervention-targeted assessments 3 months later, after which the wait-list controls will be offered PAAS as a benefit for participation in the study (IIIC.4f.1; **Fig 6**).

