#### IIIC.4f. Methods

**IIIC.4f.1. Overview:** A description of the protocol/procedures is provided (IIIC.4f.2 - IIIC.4f.6; **Fig 6, Table 1**). Eleven-to-thirteen year-old AA youth and their parents will complete information on demographic and health status as part of their clinic visits. Families selected randomly from the eligible pool will be invited to participate, while at the clinic or later via mail (**IV.A.2a, Human Subjects**). Research is an integral part of these participating clinical programs and processes are in place for a smooth transition from clinical care to research that follows the Institutional Review Board and Health Insurance Portability and Accountability Act (HIPAA) guidelines. When contact is made, they will be provided information about the study, with an overview of the time commitment and assessments. Interested families will be screened further to determine eligibility by obtaining medical, psychiatric and treatment history.

**Phase 1 (Pre-intervention Assessments):** Information on psychiatric symptoms, psychosocial factors and risky behaviors will be completed. Those who meet eligibility criteria will have a blood draw for gonadal hormones and receive training on the fMRI tasks and have a mock scan. A urine sample will be obtained to test for alcohol/drug use and pregnancy. They then will complete baseline fMRI studies. **Phase 2 (Intervention Phase):** The families will be randomized using procedures described in IIIC.4f.5 to PAAS or wait-list condition (1:1 ratio) for the 6-week intervention period. PAAS consists of 6 web- or DVD-based weekly sessions, 90 minutes per session; the first half includes individual, concurrent curricula for caregivers and youth, and the second half is a family-joint session designed for practicing the skills learned in the individual sessions. At the end of the 6-week intervention period, the urine drug test and fMRI studies will be repeated in both groups. **Phase 3 (Follow-up Phase):** Three months after the intervention phase, both psychosocial and risky-behavior assessments will be repeated. The wait-list group then will be offered the PAAS intervention as a benefit for participation in the study.

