The PAAS curriculum will likely influence the neural pathways by: 1) providing opportunities for youth to negotiate novel situations in a safe environment until they gain better adaptive skills in self-control; 2) fostering resistance-efficacy in high-risk situations, and reinforcing positive self-image and encouraging future orientation through goal-setting; and 3) encouraging youth to think about the potential consequences of risky behaviors from their parents' perspective (IIIC.3b; Table 2). Each of these pathways has evidence to suggest that reward-drive and cognitive-control/self-regulation neural circuits are involved. Parents play an important role in protecting youth against risky behaviors by providing warmth as well as consistent, inductive discipline.

Data from the computer/web, which tracks time spent on the computer and the completion of activities, will be downloaded to a secure server. Participants also will complete questions pertinent to each intervention session to ensure that they grasped the main concepts. The computer-based program was selected for the following reasons. Families can experience a computer intervention when it is most convenient for them and at their own pace. It can be accessed at home or another convenient site where a computer is available. Computer literacy and familiarity, even among those from economically-disadvantaged households, is nearly universal now. Our studies (IIIC.3b), as well as those of others, that included AA youth and adults have shown that computer-based prevention programs can be very engaging and motivating. The privacy that computer-based interventions afford is particularly important in close-knit, ethnic-minority communities, in which participants typically know one another outside the intervention context and privacy is a key concern.

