### IIIC.7. Statistical Methods

**IIIC.7a. Data Management:** Data management will be done via remote electronic data capture (*REDCap*). REDCAP was developed at VUMC to insure data integrity and completeness, including compliance with HIPAA (over 300,000 users). Data will be entered immediately after testing on data entry screens designed to duplicate the data collection forms (ACASI; **IIIC.4f.4**). Reports can be generated to track all contacts with the participants.

**IIIC.7b. Procedures for Handling Missing Data:** Missing data will be accounted for by including "missingness" as a covariate if the proportion of missing data is small, or alternatively using multiple imputation methods if the proportion of missing data is large, e.g. >5%.

**IIIC.7c. Data Reduction:** Each hypothesis will be examined using a primary variable, with supplemental information gained from analysis of other related measures (**see IIIC.5**).

**IIIC.7d. Data Analysis:** Descriptive statistics (e.g. means and standard deviations, frequencies and histograms) will be computed for all variables, along with 95% bootstrap confidence intervals. Significance tests will be two-tailed, with  $p < 0.05$ , controlling for multiple comparisons. Pubertal stage/gonadal hormones, gender and SES will be included as concomitant variables in analyses where they are known to correlate with the outcome. These covariates, while not of primary interest, will reduce residual variance and increase the precision of effect estimates for improved statistical power. Secondary analyses will determine if these covariates significantly affect the outcomes. Behavioral/emotional problem score (CBCL/YSR), lifetime history of substance use and dose of the intervention (number of completed sessions) will serve as additional potential covariates.

**IIIC.7d.1. Hypothesis 1:** PAAS will induce greater functional connectivity changes in the reward-drive and cognitive-control (fronto-striatal) circuitry compared to the wait-list condition. Post-treatment neural connectivity

scores will be regressed on group assignment (PAAS vs. wait-list) as the independent variable and baseline (pre-treatment) neural connectivity score as a covariate. Two separate models will be run for resting-state and task-based fMRI connectivity measures. Other covariates (IIIC.7d) will be included if there are group differences.

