**IIIC.7e. Power Analysis:** Statistical power was estimated with G power 3.1.9.2 software. We used traditional criteria (alpha = .05 two-tailed, power = 80%) to estimate statistical power. [Rather than base power estimates on modest pilot samples, we assessed power by *minimum detectable effect size (MDES)*.] For fMRI studies, Thirion et al. recommend sample sizes of 40 per group for reliable estimates of group differences. Given the multiple variables of interest, we selected larger sample sizes. Randomized subjects will be compared in two conditions using a multiple regression model. With N = 102 participants (after accounting for attrition), a multiple regression would have adequate power to detect an effect size as low as  $r = .31$  ( $R^2 = .10$ ). Cohen considers  $r \sim .10/.30/.50$  to be small/medium/large effect sizes. Power will be sufficient to detect medium effects. Because we will use a repeated measures model with covariates, actual power should be somewhat better. A sample size of  $n = 102$  is also sufficient to detect mediation in an analysis with medium-sized  $\alpha$  and  $\beta$  paths.

**IIIC.8. Timeline:** Table 3 shows the expected timeline of activities for the proposed research.

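### The Hypothesis 1 covariate rule, followed as written, admits sessions completed (a post-randomisation variable) into the PAAS versus wait-list model

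*Combined protocol and SAP*

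**What the plan says.** Section IIIC.7d names pubertal stage or hormones, gender and SES as covariates. It then adds behavioural problem score and lifetime substance use, and says that "dose of the intervention (number of completed sessions) will serve as additional potential covariates".

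Section IIIC.7d.1 regresses post-treatment connectivity on group and baseline connectivity, with separate resting-state and task models. It closes with "Other covariates (IIIC.7d) will be included if there are group differences". That sentence points back to the list containing dose, and its only condition is a group difference.

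The timing is in IIIC.4f.1: "At the end of the 6-week intervention period, the urine drug test and fMRI studies will be repeated in both groups". Only after the 3-month follow-up does the control arm get access: "The wait-list group then will be offered the PAAS intervention as a benefit for participation in the study". Dose is recorded during the intervention (IIIC.4f.6): "Data from the computer/web, which tracks time spent on the computer and the completion of activities, will be downloaded to a secure server".

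The target of the analysis is given in IIIC.1, "Aim 1 will assess the effects of PAAS on the magnitude of Phase 2 functional connectivity", and in the power section IIIC.7e, "Randomized subjects will be compared in two conditions using a multiple regression model". Fronto-striatal connectivity is a primary outcome (IIIC.5). The exploratory analyses in IIIC.7d.3 do not mention dose, and no other section confines it to the PAAS arm.

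**The concern.** Sessions completed is a consequence of assignment. It is zero for every wait-list youth at the outcome scan and between zero and six for PAAS youth, so the two groups differ on it whatever the data show. An analyst who applies the rule as written would add it.

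The group coefficient would then compare a PAAS youth with zero sessions against a wait-list youth. That answers neither Aim 1 nor the comparison of randomised groups on which the sample size rests. Three things can follow:

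- a real effect that works through the sessions is assigned to dose and disappears from the group term;
- precision is lost because dose and group are nearly collinear, and if every PAAS family completes six sessions then dose = 6 × group and the group effect cannot be estimated;
- if completion is related to prognosis, the group term is biased even when PAAS does nothing.

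Another analyst, taking the rule to mean baseline imbalance, would leave dose out. The two could reach opposite conclusions on Hypothesis 1 from the same data.

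**Working it through.** **The plan's own figure.** IIIC.7e gives N = 102, two-sided alpha .05, 80% power and a detectable r = .31 (R² = .10). With a noncentral F, f² = R²/(1 − R²) and noncentrality f² × N, an omnibus test with three predictors has 79.9% power at R² = .10, so the figure reproduces. The number of predictors is inferred; the plan does not state it. A one-degree-of-freedom test of group has about 90% power at partial r = .31. Attrition agrees: 128 × 0.8 = 102.4, about 51 per arm.

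**Inputs assumed, because the documents do not give them.** Baseline–outcome correlation 0.5, so residual variance is 0.75. Wait-list dose is 0. The average PAAS effect is either d = 2(.31)/√(1 − .31²) = 0.652 SD, or 0.485 SD, the value at which the model without dose has 80% power. PAAS sessions follow one of four patterns: A, 70% complete all six and the rest are uniform over 0–5; B, uniform over 0–6; C, binomial with mean 80%; D, binomial with mean 90%.

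**Precision, completion unrelated to prognosis, effect the same at every dose.** Without dose, SE = √(0.75 × 2/51) = 0.171 and power at 0.652 is about 96%. With dose, the variance of the group coefficient is multiplied by VIF = 1 + m²/(2s²), where m and s² are the PAAS-arm mean and variance of sessions. For A, m = 0.7 × 6 + 0.3 × 2.5 = 4.95 and s² = 27.95 − 4.95² = 3.45, so VIF = 1 + 24.50/6.90 = 4.55.

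| Pattern | m | s² | VIF | Power at 0.652 SD | Power at 0.485 SD |
|---|---|---|---|---|---|
| No dose in model | – | – | 1 | 96% | 80% |
| A | 4.95 | 3.45 | 4.55 | 42% | 26% |
| B | 3.0 | 4.0 | 2.12 | 73% | 48% |
| C | 4.8 | 0.96 | 13.0 | 18% | 12% |
| D | 5.4 | 0.54 | 28.0 | 11% | 8% |

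Simulation (6,000 replicates per scenario) gives 41.5/73.0/17.6/10.7% at 0.652 SD and 25.8/48.3/12.2/8.5% at 0.485 SD.

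**Other effect shapes, same simulation, average effect 0.652 SD.** If the effect is linear in sessions, the group coefficient is about 0 and rejection about 5%. If it saturates after two sessions, the coefficient is 0.32/0.30/0.65/0.66 (A/B/C/D) and power 14/21/18/11%. Without dose, power is 92–97% across all the effect shapes. With no effect and completion unrelated to prognosis, rejection stays at 5–6% with dose in the model.

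**No PAAS effect, completion correlated with the outcome residual (latent correlation ρ), dose in the model.**

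| ρ | Rejection A/B/C/D | Mean group coefficient, SD |
|---|---|---|
| 0.1 | 7–10% | – |
| 0.2 | 16/16/24/21% | −0.36/−0.25/−0.80/−1.11 |
| 0.3 | 30/32/48/44% | −0.55/−0.37/−1.20/−1.66 |
| −0.2 | 16/17/24/22% | positive |
| −0.3 | 31/32/47/44% | positive |

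For negative ρ nearly all rejections favour PAAS. Without dose, null rejection is 4.5–5.6% throughout.

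**The case against.** The strongest reply is that the plan never says dose will enter the Hypothesis 1 model. Dose is only a potential covariate, in a general paragraph serving all analyses. A rule about group differences is common shorthand for baseline imbalance, and IIIC.11 describes the IIIC.7d covariates as controls for confounding, which sessions received because of assignment are not. This stands as a limit: the finding is about what the written rule permits, not about a declared intention. It does not remove the problem, because the baseline reading is nowhere stated and dose is on the list.

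It can also be said that dose is not applicable, rather than zero, in the wait-list arm. The documents do not say how it would be scored, but zero is the natural value for a count of sessions completed by someone offered none. The voxel-wise comparison in IIIC.4f.2b.6 names no dose covariate, but that does not cure IIIC.7d.1.

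The sizes do rest on assumed completion patterns, effect shapes and correlations. The r = .31 in IIIC.7e is not clearly a group effect, which is why the 0.485 SD version is shown beside it. The link between completion and prognosis is only a possibility, supported by the self-paced format: "Families can experience a computer intervention when it is most convenient for them and at their own pace".

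Finally, IIIC.4f.2b.6 allows scan-motion metrics as covariates, and those from the second scan are post-randomisation. They are not on the IIIC.7d list, so the qualifier proposed here leaves them alone.

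**Conclusion.** The concern holds for Hypothesis 1. Read literally, the inclusion rule puts into the randomised comparison a variable that is determined after randomisation and nearly collinear with group. The loss of the Aim 1 estimand follows from the design once wait-list dose is scored zero; it needs no further assumption.

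The numerical harm depends on facts the plan does not give. If completion is unrelated to prognosis, type I error is preserved; the cost is low power or, for an effect linear in sessions, a group estimate near zero. If completion is related to prognosis, the group estimate is biased, downwards when better-prognosis families complete more and in favour of PAAS when worse-prognosis families do. The model without dose has neither problem. Because a primary-outcome conclusion could turn on the reading chosen, the wording should be settled before analysis.

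**What to change.** In IIIC.7d, add: *Sessions completed is measured after randomisation and will not enter any PAAS versus wait-list model; these comparisons are analysed as randomised.* In IIIC.7d.1, limit the other covariates to those measured before randomisation.

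If dose is of interest, use it only in a labelled supplementary description within the PAAS arm, or in a complier-type analysis with randomised assignment as the instrument.

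The cost is one sentence and a short qualifier, with no new data. If the baseline reading was always intended, the planned Hypothesis 1 analysis does not change.

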**IIIC.4f.3h. Physical/Laboratory Measures:** Participants will rate their pubertal status based on the illustrations of stages of pubertal development. Blood will be drawn for serum gonadal steroids (estradiol, progesterone and testosterone). In exploratory analyses, we will examine the effect of pubertal stage and gonadal hormones on neural responses, as there likely will be a greater variation in pubertal maturation at this age range (11-13 years). A urine test will provide qualitative and quantitative information on substance use (amphetamines, benzodiazepines, cannabinoids, cocaine, ethanol, opiates, oxycodone, and phencyclidine). Sexually active females will have a urine test to rule out pregnancy for the MRI studies.

**IIIC.4f.4. Data Collection Protocol:** Trained staff members will conduct the assessments. They will have a minimum of 40 hours of training and supervised practice on how to obtain informed assent/consent, build rapport, interview, and assist participants on the computer-based data collection system and PAAS-technology program. Data collection will occur at clinical sites, the PI's lab, participants' homes or community settings, based on the participants' choices. Families will use the computer-based data system to complete assessments using audio computer-assisted self-interview (ACASI) procedures, which are integrated into the remote data management system (IIIC.7a). Each computer will have headphones, the computer screen will display one question at a time, and all information that appears on-screen also will be read to participants by the computer. Compared with face-to-face interviews and self-administered surveys, ACASI offers privacy and confidentiality that, in turn, elicits less social desirability bias, and more accurate reports on questions about sensitive issues or negative behaviors. The use of ACASI in our previous studies reduced missing data, increased consistency and eliminated literacy requirements. Psychiatric diagnostic interviews will be conducted by trained research assistants. [name] was involved in the development and testing of the K-SADS-PL. Prior to initiating the study, reliability will be assessed (requiring  $\geq 85\%$  agreement). In order to avoid reliability drift over time, reliability checks will be made annually. All interviews will be audio-taped, and a random selection of 15% of the interviews will be co-rated by [name].

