**IIIC.4f.5. Randomization:** A 2 (gender) x 2 (Tanner stage) x 2 (intervention) randomized, matched-pairs, block-design will be used to stratify participants based on gender and Tanner stage (I-II, III-V) comprising 4 blocks for 128 participants. Within each block, 16 pre-randomized (PAAS or wait-list) pairs based on order of intake will be prepared in advance. Randomization will proceed as follows: the first youth to enter the study in each block will be assigned to either PAAS or wait-list (based on pre-randomization for that pair) and the second will be assigned to the opposite condition. The third youth will be assigned to either PAAS or wait-list (based on pre-randomization for that pair) and the fourth will be assigned to the opposite condition. The randomization based on the order of entry will continue in this manner until all matched pairs within each of the 4 blocks are filled.

**IIIC.4f.6. PAAS Protocol:** PAAS is a 6-week, technology-delivered, family-based youth risk intervention program (Table 2). PAAS uses a set of six (one per week) DVDs or the web to deliver separate sessions for parents and youth, and joint sessions in which they both engage on the same computer to integrate and practice the skills they have just learned in their separate sessions. Each weekly session takes about 45 minutes to complete, for an average of 90 minutes per participant (45 minutes separate plus 45 minutes joint), and a total of 9 hours for the 6-week intervention. Each session includes a review, a virtual discussion, and observing and interacting with four parent and four youth Avatars that reflect phenotypes of AAs, with voice-overs by AA parents and youth. Videos portraying family interactions and intrapersonal processes are integrated into each session to convey key points of the intervention along with interactive activities to promote skill-building and to reinforce learning. PAAS also includes a technology tutorial and an introductory session. After receiving detailed instructions face-to-face, the program will be accessible through a website to participants who prefer using the Internet, or it will be downloaded onto laptop computers and delivered to them at their homes or other locations convenient to the participants, such as participating clinics or community settings (e.g. churches, community centers).

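### The plan gives two conflicting rules for adding covariates to the Hypothesis 1 models, and neither guarantees adjustment for the gender-by-Tanner strata used in randomisation

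*Combined protocol and SAP*

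**What the plan says.** Two rules stand close together in the statistical methods.

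- **IIIC.7d, Data Analysis:** "Pubertal stage/gonadal hormones, gender and SES will be included as concomitant variables in analyses where they are known to correlate with the outcome". The stated purpose is to reduce residual variance and gain precision. The section adds: "Secondary analyses will determine if these covariates significantly affect the outcomes". It then lists behaviour-problem scores, lifetime substance use and the number of sessions completed as further possible covariates.
- **IIIC.7d.1, Hypothesis 1:** post-treatment connectivity is regressed on arm and baseline connectivity, in separate models for rest and task. Then: "Other covariates (IIIC.7d) will be included if there are group differences".

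The randomisation section (IIIC.4f.5) says a matched-pairs design "will be used to stratify participants based on gender and Tanner stage (I-II, III-V) comprising 4 blocks for 128 participants". Each block holds 16 pre-randomised pairs. Within a pair the first youth gets the pre-assigned arm and "the second will be assigned to the opposite condition".

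On whether puberty is already known to matter, IIIC.4f.3h says: "In exploratory analyses, we will examine the effect of pubertal stage and gonadal hormones on neural responses".

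**The concern.** The two rules disagree about a covariate that is prognostic but balanced. The first admits it and the second leaves it out. Pairing within gender-by-Tanner strata makes exactly those factors balanced, so the conflict falls on the variables the trial chose to randomise by.

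The first rule does not clearly rescue them. It requires a known relation to the outcome, while pubertal effects on neural responses are assigned to exploratory analysis and covariate effects on outcomes to secondary analysis.

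Two things are at stake:

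- **Efficiency.** Stratified randomisation removes between-stratum variation from the difference between arms. A model without the strata still counts that variation as residual error, so the reported standard error is too large and the test is conservative.
- **Pre-specification.** No test or threshold defines a difference between arms, so the form of a primary model can be settled after the data are seen.

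**Working it through.** **1. The plan's own figures (IIIC.6, IIIC.7e).** 128 × 0.8 = 102.4, so N = 102. At two-sided alpha .05 and 80% power the plan says "a multiple regression would have adequate power to detect an effect size as low as" r = .31 (R² = .10).

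- An overall R² test with 3 predictors gives a minimum detectable R² of .100 (r = .316), which matches the stated R². The plan does not state the number of predictors.
- A one-degree-of-freedom test of the arm term alone gives r = .27, and about 90% power at r = .31. That is the test Hypothesis 1 uses.
- With 1:1 allocation, d = 2r/√(1 − r²) = 0.62/√(1 − 0.0961) = 0.652.

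**2. How often would an arm difference be found on gender or Tanner stage?** The paired scheme (4 strata × 16 pairs) was simulated for 12,000 trials per dropout pattern.

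| Dropout pattern | Definition of a difference | Trials in which gender or Tanner enters |
|---|---|---|
| Random, 128 to 102 | chi-square p < .05 | 0 |
| Random, 128 to 102 | chi-square p < .20 | 93 (93/12,000 = 0.8%) |
| Random, 128 to 102 | standardised difference > .10 | 47% |
| 30% vs 10% by arm | chi-square p < .05 | 2 |
| 40% in PAAS boys, 13% in all others | chi-square p < .05 | 178 (178/12,000 = 1.5%) |

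A separate simulation with random dropout put the p < .05 rate at 0.005% to 0.008%. Under unstratified randomisation it would be about 10% for either factor. So a significance test almost never admits the strata, while a standardised-difference rule admits one of them in nearly half of trials.

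**3. What omission costs.** Let R be the share of variance left after baseline connectivity that the strata explain. The documents give no value, so a range is assumed. To a first approximation the reported standard error is inflated by 1/√(1 − R):

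- R = .02: 1/√.98 = 1.010
- R = .05: 1/√.95 = 1.026
- R = .10: 1/√.90 = 1.054
- R = .20: 1/√.80 = 1.118

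The table below simulates the paired scheme with 26 of 128 lost at random. The outcome is regressed on arm and baseline, without and with 3 stratum indicators, in 8,000 trials per setting.

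| R (assumed) | Excess in reported SE | Type I error without strata | Power at d = .652, without / with | Power at d = .5, without / with |
|---|---|---|---|---|
| 0 | 0% | .050 | .90 / .90 | .70 / .70 |
| .02 | 1% | .048 | .90 / .90 | .71 / .71 |
| .05 | 2% | .047 | .90 / .91 | .70 / .71 |
| .10 | 5% | .042 | .92 / .93 | .70 / .74 |
| .20 | 12% | .033 | .92 / .95 | .72 / .80 |

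Power forgone, taken before rounding, is 0/0/1/2/3 points at d = .652 and 0/0/2/4/8 points at d = .5. With strata in the model, type I error was .049 to .052 throughout. Simulation error on a type I rate is √(.05 × .95/8,000) = .0024, so the figures for R up to .05 cannot be told apart from .050.

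At R = .20 the true SD of the estimate hardly moves (.184 without, .180 with), but the reported standard error is .199 without and .179 with. The estimate is sound; its stated precision is not.

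**4. Cross-check.** A separate simulation with 40,000 null trials per setting gave type I error of .052, .044, .042 and .032 at R = 0, .05, .10 and .20 without strata. With full retention the large-sample size is 2[1 − Φ(1.96/√(1 − R))]. This equals .044, .039 and .028 at R = .05, .10 and .20. Dropout breaks some pairs and pulls the size part of the way back to .05. At d = .56, which gives 80% power without strata, power without and with adjustment was 80.0% and 79.8% at R = 0, 80.0% and 82.9% at R = .10, and 81.4% and 87.4% at R = .20.

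**The case against.** **A narrower reading removes the conflict.** IIIC.7d has two tiers, and the sentence in IIIC.7d.1 could refer only to the second one (behaviour problems, substance use, sessions completed). This is possible, but the sentence cites IIIC.7d as a whole. Even on the narrow reading the strata enter only if known to be prognostic, so they are still not guaranteed.

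**The plan clearly intends prognostic adjustment.** IIIC.7d says covariates will improve precision, and IIIC.7e expects better power because of them. IIIA.2 and IIIC.4d link reward-system activity to puberty, which could support entry under the first rule. The exploratory and secondary analyses are also compatible with having the terms in the model. All of this is fair. It shows the wish for adjustment, and is a reason to write it down, but it does not settle which rule applies to Hypothesis 1.

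**The effect is small and conditional.** This stands. At r = .31 no more than about 1 point of power is lost up to a 5% share. The 8-point figure needs both d = .5 and a 20% share, and no document supports that share.

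**A significance test is an assumption.** This also stands. The plan does not say that a difference between arms means p < .05, so the claim that the strata rarely enter holds only for that definition. The missing definition is itself part of the problem.

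**The simulation is not the full planned analysis.** It uses complete cases and one connectivity score. The plan also has voxelwise maps (IIIC.4f.2b.6) and multiple imputation (IIIC.7b). The figures illustrate the regression described in IIIC.7d.1 and should not be read as exact operating characteristics.

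**Conclusion.** The concern holds. IIIC.7d and IIIC.7d.1 set different conditions for the same covariates, and neither secures adjustment for the randomisation strata. If a difference between arms means a significance test, the strata will almost never enter, and the Hypothesis 1 test is mildly conservative to the extent that they are prognostic. For an assumed share up to 10%, the reported standard error is at most about 5% too wide and type I error is about .042 or higher. At 20% the figures are 12% and about .033.

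The consequence is lost efficiency and an open model form. The treatment estimate is essentially unaffected and false positives do not increase. The sizes rest on an assumed strata share, mostly random dropout and complete-case analysis of a single score. The conflict between the rules and the undefined trigger rest on no assumption about that share. This should be corrected, but it does not threaten the validity of the trial.

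**What to change.** 1. In both Hypothesis 1 models (rest and task), include the four-level gender-by-Tanner stratum (I–II, III–V), as used at randomisation, alongside arm and baseline connectivity, whatever the observed balance.
2. Delete the arm-difference trigger from IIIC.7d.1.
3. Reconcile IIIC.7d with IIIC.7d.1: name any further covariates before the data are seen, chosen for their expected relation to the outcome and not for imbalance.
4. Restrict that list to baseline variables. The number of sessions completed is measured after randomisation. If wait-list youth are coded as zero sessions, it differs by arm by construction, so the present trigger could admit it. At an assumed 70% to 95% completion per session, its correlation with arm would be .94 to .99.

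The cost is SAP wording only, with no new data. Residual degrees of freedom go from 102 − 3 = 99 to 96. If the strata turn out not to be prognostic, less than 1 point of power is lost (80.0% against 79.8% at d = .56).
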